12.1. Efficacy analysis

The following parameters will be summarized by cohort and overall (if appropriate) on the Efficacy population:

- Best Overall Response
- Disease Control Rate
- Objective Response Rate
- Duration of response (DoR)
- Progression Free survival (PFS);
- Overall Survival (OS).

ORR locally assessed is the primary endpoint of the Cohort Expansion Phase. All efficacy

endpoints related to tumour assessment will be evaluated considering both local (secondary endpoints) and central (exploratory endpoints) radiology assessments.

Best Overall Response (BOR) is derived as follows:

- If a subject has at least one overall response of CR, then BOR is CR;
- If a subject doesn't have any overall response of CR but has at least one overall response of PR, then BOR is PR;
- If a subject doesn't have any overall response of CR or PR but has at least one overall response of SD (or Non-CR / Non-PD) at least six weeks after the first intake of MEN1611, then BOR is SD (or Non CR / Non PD);
- If a subject doesn't have any overall response of CR, PR, SD (or Non-CR / Non-PD) after at least 6 weeks from the first intake of MEN1611, but has at least one overall response of PD, then BOR is PD;
- In all other cases, BOR is NE.

Objective Response Rate (ORR) is calculated as the sum of BOR rates of complete response (CR), partial response (PR).

Disease Control Rate (DCR) is calculated as the sum of BOR rates of complete response (CR), partial response (PR) and stable disease (SD).

Overall Survival (OS) is calculated as:

- In case of all-cause death:
OS = date of death - date of first study treatment administration + 1;
- In case of censored information not for drop-out:
OS = date of end of observation period (i.e. maximum between end of study and last follow up date) - date of first study treatment administration + 1;
- In case of censored information for drop-out:
OS = last available date in eCRF - date of first study treatment administration + 1.

Progression-free Survival (PFS) is calculated as:

- In case of death/disease progression:
PFS = date of death or date of first disease progression - date of first study treatment administration + 1
For subjects who experienced both death and progression disease, the date referred to the event that came first is considered.
- In case of censored information due to responding subjects or lost to follow-up:
PFS = date of censoring - date of first study treatment administration + 1

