Detailed censoring rules are as follows:

Circumstances		Options for end-date (progression or censoring)	Outcome
1	Documented Progression	(i) Date of documented progression	Progressed
2	Death without documented progression	(i) Date of death	Progressed
3	Documented progression or death after exactly one missing assessment	(i) Date of progression or death	Progressed
4	Documented progression or death after two or more missing assessments	(i) Date of last adequate assessment ^a	Censored
5	No documented progression and no death (with at least one post baseline assessment)	(i) Date of last adequate assessment	Censored
6	Treatment discontinuation Reason ' Disease progression/clinical progression/progression ' without radiological assessment.	(i) Ignore clinical progression and follow situations above	As per above circumstances
7	No baseline tumor assessment	Date of first study treatment administration	Censored
8	No post baseline assessment and no death	Date of first study treatment administration	Censored
9	Subject lost to follow-up (or withdrew consent) before documented progression or death	(i) Date of last adequate assessment	Censored

^aAfter the last adequate tumor assessment. Date of next scheduled assessment- as specified in the protocol

Duration of Response (DR) is calculated as:

- In case of disease progression:
DR = date of disease progression – date of first occurrence of a BOR of PR, CR or SD + 1
- In case of censored information:
DR = date of last tumor assessment – date of first occurrence of a BOR of PR, CR or SD + 1

Note: subjects with only one assessment post baseline with response equal to PD won't be counted for the DR calculation

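### The best-overall-response rule in SAP 12.1 has no cut-off at first progression or new anticancer therapy, so a later scan can override PD; the main exposure is the central read

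*SAP*

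**What the plan says.** SAP 12.1 sets out BOR as a hierarchy:

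- CR: "If a subject has at least one overall response of CR, then BOR is CR".
- PR: a subject who "doesn't have any overall response of CR but has at least one overall response of PR, then BOR is PR".
- SD: a subject without CR or PR who "has at least one overall response of SD (or Non-CR / Non-PD) at least six weeks after the first intake of MEN1611". This limb has a lower time limit but no upper one.
- PD: a subject with none of the above, "but has at least one overall response of PD, then BOR is PD".

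ORR adds the CR and PR rates of BOR; DCR adds CR, PR and SD. The same section states that "ORR locally assessed is the primary endpoint of the Cohort Expansion Phase". It also has all tumour-assessment endpoints evaluated on both the local and the central read, the latter labelled exploratory, and gives one BOR rule for both.

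PFS in SAP 12.1 runs to the first progression or death. Neither the BOR text nor the censoring table mentions new anticancer therapy.

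**The concern.** BOR and PFS use different windows on the same scans. Once a patient has progressed, the hierarchy still looks at everything that follows, and any better reading outranks the PD. For ORR and DCR the error has one direction: later scans can add a success but never remove one. The same patient can then be a responder, or a disease-control success, and also have a PFS event dated before that response.

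Efficacy is purely descriptive (SAP 12), so the reported rates are themselves the result. No type I error or power is at stake. What matters is whether ORR and DCR mean what a reader takes them to mean, and whether the local and central tables can be compared.

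**Working it through.** The documents give no figure to reproduce: the sample-size sections are redacted or blank, and no test is planned. The check has four steps.

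**1. Apply the rule literally, and again cut at first PD.** Scans fall on Day 1 of Cycles 3, 5 and 7 (Protocol 8.5.1), that is, study days 2×28+1 = 57, 4×28+1 = 113 and 6×28+1 = 169.

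| Sequence of overall responses | BOR as written | BOR cut at first PD | PFS event | Change due to later scan |
|---|---|---|---|---|
| PD d57, PR d113 | PR | PD | d57 | ORR and DCR up |
| PD d57, SD d113 | SD | PD | d57 | DCR up |
| SD d57, PD d113, PR d169 | PR | SD | d113 | ORR up, DCR unchanged |
| SD d57, PD d113, SD d169 | SD | SD | d113 | none |
| PR d57, PD d113 | PR | PR | d113 | none |
| PD d57 only | PD | PD | d57 | none |

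**2. Can this happen on the local read?** Disease progression ends treatment (Protocol 8.2.3.2), and scheduled scans run until progression or the End of Study Visit (Protocol 8.5.5.2). The End of Study scan is done only if the last one is more than 8 weeks (56 days) old (Protocol 8.5.1). With PD on a scheduled scan and dosing stopped at that visit, the longest gap from scan to End of Study Visit is 7 (scan window) + 28 (four weeks after last dose) + 7 (visit window) = 42 days. Since 42 < 56, no further scan is triggered. One would be triggered only if dosing went on more than 56 − 42 = 14 days past the visit. Otherwise it takes an unscheduled scan, and SAP 11.3 does bring a last unscheduled scan into the analysis, as the End of Study assessment.

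Very early progressors also drop out of the denominator. The Efficacy population needs two complete cycles, 2×28 = 56 days (SAP 7.3). A patient withdrawn for local PD at week 5 (day 35) does not reach that.

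**3. Can this happen on the central read?** Images are uploaded for retrospective central analysis (Protocol 8.5.1), so a central PD does not stop treatment. If the site has not called PD, scans continue every two cycles.

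- A later central CR or PR raises central ORR.
- A later central SD raises central DCR only if no qualifying central SD (and no CR or PR) came before the central PD. The earliest on-schedule scan is day 57 − 7 = 50, which is 49 days after first intake and already beyond six weeks (42 days). A patient with central SD on that scan keeps BOR = SD with or without the cut-off (fourth row). Only central PD at or before the first qualifying scan, not called by the site, can move DCR through a later SD.

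**4. Size per patient.** The protocol synopsis (Study Duration) gives up to 40 patients evaluable for efficacy. One patient is 1/40 = 2.5 points, and more if fewer are evaluable. For illustration, assume 6 true responders and use exact (Clopper-Pearson) 95% intervals, which the SAP does not itself plan for ORR:

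| Reclassified | ORR | 95% interval |
|---|---|---|
| 0 | 6/40 = 15.0% | 5.7–29.8% |
| 1 | 7/40 = 17.5% | 7.3–32.8% |
| 2 | 8/40 = 20.0% | 9.1–35.6% |

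**The case against.** The strongest reply is that protocol conduct already closes the gap. On the local read this is nearly right. Treatment and scheduled scans stop at PD, the End of Study scan is not triggered, and early progressors leave the Efficacy population. Other anticancer treatment is also prohibited during the study (Protocol 8.4.8), so a scan after new therapy but before the End of Study Visit needs a deviation. These are rules of conduct, however. None of them removes a later scan from the BOR derivation if one exists.

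A second reply is that the endpoint is defined by RECIST v1.1 and that the central committee works to its own charter. Neither document states a BOR window, and the derivation written out in SAP 12.1 is what will be programmed. The BIRC Charter (Protocol 8.8) was not supplied. If it stops reads at central PD, the central exposure disappears. Attachment A, also not in the supplied text, is cited in SAP 5.4.2 for censoring rules, not for BOR.

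Third, response by timepoint is tabulated and listed for both reads (Tables 3.2.1 and 3.2.2, Listings 5.29 and 5.30), so an affected patient could be traced. That stands, but it does not correct the summary rates.

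Three stronger readings are tempting and are not supported:

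- **That the primary ORR is materially inflated.** Step 2 of the check shows that on-protocol conduct produces no post-PD local scan.
- **That every patient with central PD before local PD can add to central DCR.** Those with an earlier qualifying central SD do not change. The documents give no discordance rate, so any total in percentage points would rest on invented inputs.
- **That duration of response must come out negative.** Under "In case of disease progression" the SAP uses the date of disease progression without saying first. PD on day 57 and PR on day 113 give 57 − 113 + 1 = −55 days only if first progression is meant. SAP 5.4.2 runs the duration until progression is shown, which fits a PD after the response. On that reading the duration is positive, but it belongs to a response that began after the PFS event.

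**Conclusion.** The gap is real: as written, the BOR rule lets an assessment after PD, or after new anticancer therapy, outrank the PD, and it is out of step with PFS in the same section. For the locally assessed primary ORR the expected effect is about zero on protocol; it arises only through unscheduled scans or deviations. The main exposure is the exploratory central read: central ORR through a later CR or PR, and central DCR through a later SD in patients with no qualifying central SD before central PD.

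Each such patient is worth 2.5 points at n = 40, always upward. The number affected cannot be derived from the documents. The central part assumes that reads continue after central PD, which the BIRC Charter would settle. This is a drafting correction to make before database lock, not a threat to the trial's primary result.

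**What to change.** Add to SAP 12.1, ahead of the BOR hierarchy and applying to every limb (CR, PR, SD or Non-CR/Non-PD, PD):

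> BOR, and hence ORR, DCR and duration of response, is derived from overall responses up to and including the first documented PD and before the start of any new anticancer therapy, whichever comes first, separately for the local and the central read. Later assessments are listed but not used.

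With this window, BOR and PFS treat first progression in the same way, and no response or duration of response can start after PD. Check that the BIRC Charter uses the same stopping point.

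The cost is one sentence and a date filter in the BOR program. No new data are needed: concomitant medication is already recorded up to the End of Study Visit (Protocol 8.4.8). ORR or DCR may come out slightly lower than under the literal rule.

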8.2.4 End of Study

After the End of Study Visit, all patients evaluable for efficacy will be followed for survival status according to local practice (a visit or a telephone call) every 12 weeks up to the end of study.

The study ends with the End of Study Visit of the last patient who discontinues the study treatment. For safety monitoring, all serious adverse events (SAEs) with a suspected causal relationship to the study treatment that occur after the End of Study must be recorded and notified to the Sponsor.

All biological samples except for safety blood samples collected along the study will be stored for a maximum of 10 years from the date of the Last Patient Last Visit. After 10 years, the samples will be destroyed.

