12 END OF CLINICAL STUDY AND ARCHIVING

[figure not shown]
The clinical study will end with the collection and analysis of study data and the issue of the clinical study report. All essential documents will be archived by the Sponsor according to the relevant SOP.

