5.4.2. Secondary endpoints

- *Safety and tolerability:*
 - Incidence, severity as per CTCAE v. 5.0 grading, seriousness and treatment-causality of TEAEs.
 - Frequency of clinically significant abnormalities in physical examination, safety laboratory tests, urinalysis, vital signs and 12-lead ECG.
- *PK profile:* MEN1611 plasma concentration-time data will be summarised descriptively.
- *Disease Control Rate (DCR)* defined as percentage of patients whose disease shrinks or remains stable over a certain time period. DCR is the sum of the BOR of complete, partial and stable disease rates according to local assessment.
- *Objective Response Rate (ORR)* defined as percentage of patients who had a BOR of complete response (CR), or (PR) partial response to therapy.
- *Duration of response* defined as time from first occurrence of a BOR of PR, CR or SD as locally assessed, until the disease has been shown to progress following treatment. Subjects, with a previous response, who do not show a relapse or die without recording a relapse are censored at their last available relapse-free tumor assessment date. Subjects with only one tumor assessment after baseline showing a PD, are not included in the calculation. Please refer to Attachment A for the complete Censoring Rules list.
- *Progression Free Survival:* Defined as the number of days between the first study treatment

administration to the date of first documented disease progression as per local assessment, relapse or death from any cause. Responding patients and patients who are lost to follow-up are censored at their last tumour assessment date. Please refer to Attachment A for the complete Censoring Rules list.

- *Overall Survival:* Defined as the number of days between the first study treatment administration and death from any cause. Patients still alive, that have withdrawn the study, are censored using the latest among end of study and follow-up dates. Drop-out patients are considered censored and the last available date in which the subject is known to be alive will be considered.

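### For drop-outs, SAP 12.1 censors overall survival at the latest eCRF date while SAP 5.4.2 uses the last date known alive, so OS may be overstated when the two dates differ

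*SAP*

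**What the plan says.** The protocol (8.5.5.2) defines OS from first study treatment to death from any cause and gives no censoring rule for it. The SAP supplies the rules, in two places.

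- **Drop-outs, SAP 5.4.2:** "Drop-out patients are considered censored and the last available date in which the subject is known to be alive will be considered".
- **Drop-outs, SAP 12.1:** "OS = last available date in eCRF - date of first study treatment administration + 1". Nothing requires that date to show the patient alive.
- **Other living patients, SAP 5.4.2:** "Patients still alive, that have withdrawn the study, are censored using the latest among end of study and follow-up dates".
- **Other living patients, SAP 12.1:** "OS = date of end of observation period (i.e. maximum between end of study and last follow up date", counted from first treatment.

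The pointer in 5.4.2 to a full list of censoring rules (Attachment A) is attached to duration of response and PFS, not to OS. The censoring table in 12.1 also concerns progression. Neither settles the OS question.

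**The concern.** Section 12.1 holds the formula, so it is the likelier one to be programmed. The latest date in an eCRF need not be a date on which the patient was seen or spoken to. SAP 11.5.2, on cetuximab treatment duration, lists the date last known alive and the date of withdrawal from the study as separate items, so the plan itself treats them as different dates.

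If a drop-out is censored at a later administrative date, that patient stays in the Kaplan-Meier denominator over an interval in which a death would not have been known. Two programmers, one working from 5.4.2 and one from 12.1, could each follow the SAP and produce different OS curves. The trial is single-arm, so no control arm carries the same distortion.

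**Working it through.** **No plan figure to reproduce.** The documents state no OS median, survival rate, event count or drop-out rate, and the sample-size section is redacted. The check is therefore a comparison of rules plus an illustration on assumed inputs.

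**Mechanism.** Take a hypothetical drop-out last seen alive on study day 150, whose loss to follow-up is recorded on day 234. The 5.4.2 rule gives OS = 150 days, censored. The 12.1 rule gives 234 days, censored. The gap is 84 days; at the SAP's 30.4375 days per month (7.2.1), 84 / 30.4375 = 2.76 months. The 84 days match the 12-week survival-contact interval in Protocol 8.5.1. Suppose one death occurs in that interval among 20 patients truly under observation. The survival factor should be 1 − 1/20 = 0.950; with the drop-out still counted it is 1 − 1/21 = 0.952.

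**Direction for drop-outs.** If the date last known alive is itself in the eCRF, the latest eCRF date cannot precede it. The 12.1 result is then equal to or longer than the 5.4.2 result.

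**Illustrative size.** Assumptions, none from the documents:
- exponential OS with median 6, 9 or 12 months;
- 10%, 20% or 30% of patients assigned a drop-out time uniform over 0 to 12 months;
- administrative follow-up of 6 to 24 months;
- latest eCRF date 1 or 2.76 months after last known alive for every drop-out;
- 40,000 simulated patients per scenario.

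The table gives the result with the gap minus the result at last known alive, as a range over the three medians.

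| Assigned drop-out | Actually censored as drop-outs | Gap (months) | Change in 12-month OS (points) | Change in median (months) |
|---|---|---|---|---|
| 10% | 5% to 7% | 1 | +0.3 to +0.4 | +0.05 to +0.13 |
| 10% | 5% to 7% | 2.76 | +0.8 to +0.9 | +0.14 to +0.28 |
| 20% | 10% to 13% | 1 | +0.6 to +0.7 | +0.10 to +0.22 |
| 20% | 10% to 13% | 2.76 | +1.7 to +1.9 | +0.26 to +0.60 |
| 30% | 15% to 20% | 1 | +1.0 to +1.1 | +0.16 to +0.41 |
| 30% | 15% to 21% | 2.76 | +2.8 to +3.1 | +0.43 to +1.11 |

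Example: median 9 months, 20% assigned, gap 2.76 months. 12-month OS goes from 39.7% to 41.6% (+1.9 points) and the median from 9.01 to 9.44 months.

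Simulated trials of 40 patients, the protocol's target for efficacy evaluation, agree. With an assumed median of 9.5 months, 20% drop-outs and a 3-month gap, 12-month OS is 43.8% against 41.7%, a difference of 2.1 points.

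**The case against.** **The effect may be nil or minor.** The documents do not show that a drop-out's latest eCRF date is anything other than a visit. Central laboratory and central imaging results reach the sponsor by separate transfers (Protocol 10.1.4 and 10.1.5), so late report dates may never enter the eCRF. The drop-out rates and gaps above are invented. At n = 40 the sampling error of a 12-month OS near 41.7% is about √(0.417 × 0.583 / 40) = 7.8 points, well above any shift in the table. OS is secondary and descriptive (SAP 12). All of this stands and limits the weight of the point. It does not remove the contradiction between the two rules. Sampling error also does not excuse a rule whose error, where there is one, runs one way.

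**A reader might infer that 5.4.2 and 12.1 also conflict for other living patients.** They do not: both take the later of end of study and last follow-up.

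**A reader might infer that those patients are credited with survival up to the trial's end.** Protocol 8.2.4 does use the term at trial level: "The study ends with the End of Study Visit of the last patient who discontinues the study treatment". Chapter 12 has another version: "The clinical study will end with the collection and analysis of study data and the issue of the clinical study report". But Protocol 8.5.1 also has a patient-level End of Study Visit four weeks after the last MEN1611 dose, at which the patient is examined, and SAP 11.3 and 11.5.3 use the term at patient level. Survival follow-up comes after that visit, so on this reading the maximum is a working last-contact rule. The Chapter 12 event follows database lock and cannot sensibly be a censoring date.

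Even on the trial-level reading, the direction of error is open. In simulated trials of 40 patients (median 9.5 months, 24 months' accrual plus 6 months' follow-up, contacts every 84 days, true 12-month OS 41.7%):
- If deaths are learned only at contacts, trial-end censoring gives 43.1% and last-known-alive 41.6%.
- If deaths are learned when they occur, trial-end censoring gives 41.6% and last-known-alive 40.2%.

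The documents do not say which applies. What remains here is a term that needs a definition.

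**Conclusion.** The SAP gives two different OS censoring dates for drop-outs, and the one in the formula does not require evidence that the patient was alive. That should be corrected. Whether it changes the result is conditional: the difference is zero if the latest eCRF date is a true contact, and upward otherwise. Under the assumed rates and gaps, the upward shift is about 0.3 to 3.1 points in 12-month OS and 0.05 to 1.1 months in the median.

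The documents do not support saying that OS is certainly overstated. Nor do they support extending the conflict to living patients who are not drop-outs. The SAP does not say how a drop-out differs from a patient who has withdrawn from the study, which is a further reason to make both rules return the last contact. The primary response rate is unaffected.

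**What to change.** In SAP 12.1, replace the drop-out formula with the 5.4.2 rule:

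*OS = min(last date documented alive, data cut-off) − date of first study treatment + 1, censored.*

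List the eCRF dates that count as evidence of life: an attended visit, a dose given at site, a scan, a sample drawn, a successful survival contact. State that the date a withdrawal or loss to follow-up was recorded does not count by itself.

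For other living patients, keep the maximum in both sections, and state that end of study there means the patient's own End of Study Visit, where it took place. The maximum with the last follow-up date is then the last contact.

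The cost is SAP wording, to be settled before database lock. No extra round of survival calls is needed. Reported OS may come out slightly less favourable.

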
Study Duration
 
The overall study duration will depend on the completion of the dose levels/cohorts, the number of patients to be treated per each dose-cohort and the completion of Step 2 up to a total of 40 evaluable patients for efficacy.
 
All patients pre-screened for the PIK3CA mutation will undergo a maximum 4 weeks Screening Period.
 
Each treatment cycle will last 28 days.
 
Individual study duration will depend on the duration of the study treatment which continues up to disease progression or study discontinuation for other reasons.
 
The End of Study Visit will be performed 4 weeks after the last dose of MEN1611.
 
Survival Follow-up:
 
After the End of Study Visit, all patients evaluable for efficacy will be followed for survival status according to local practice (a visit or a telephone call) every 12 weeks up to the End of Study.
 
End of Study:
 
The study ends with the End of Study Visit of the last patient who discontinues the study treatment.
 
For safety monitoring, all serious adverse events (SAEs) with a suspected causal relationship to the study treatment that occur after the End of Study must be recorded and notified to the Sponsor.
	

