8.5.5.2 Secondary Endpoints

- Safety and tolerability:
 - Incidence, severity as per CTCAE v. 5.0 grading, seriousness and treatment-causality of TEAEs.
 - Frequency of clinically significant abnormalities in physical examination, safety laboratory tests, urinalysis, vital signs and 12-lead ECG.
- PK profile: MEN1611 plasma concentration-time data will be analysed using a population PK approach. A nonlinear mixed effects model will be used to determine population PK parameters and their associated variabilities (e.g. CL/F, V/F, Ka). Individual PK parameters (e.g. AUC, Cmax) will be estimated using a post hoc analysis.
- Disease Control Rate (DCR) defined as percentage of patients whose disease shrinks or remains stable over a certain time period. DCR is the sum of the complete, partial and stable disease rates according to local assessment.
- Duration of response defined as time from confirmation of a PR, CR or SD as locally assessed, until the disease has been shown to progress following treatment.
- PFS: Defined as the number of days between the first study treatment administration to the date of first documented disease progression as per local assessment, relapse or death from any cause. Responding patients and patients who are lost to follow-up are censored at their last tumour assessment date.
- OS: Defined as the number of days between the first study treatment administration and death from any cause.

For the baseline assessment, CT scan or MRI should be performed no more than 4 weeks before the start of study treatment. Follow-up assessment will be performed every 2 cycles during study treatment starting from Day 1 Cycle 3 (within a window of 7 days before the visit date) until objective disease progression as defined by RECIST v1.1 or at the End of Study Visit. Any other site at which a new disease is suspected should be appropriately imaged. If an unscheduled assessment is performed and the disease has not progressed, subsequent assessments should be performed at their scheduled visits.

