3.1. Changes from study protocol

All analyses detailed in this document are as specified in the protocol and subsequent amendments, no major changes from the protocol-planned primary analysis have been performed. The only exception is the PK data analysis, for which no estimation of individual PK parameters will be conducted by using a population PK approach. Plasma concentrations of MEN1611 by time-point will be summarised by descriptive statistics only.

4. Study overview

MEN1611 is a potent and selective Class I PI3K inhibitor with a novel structure. In particular, it has potent inhibitory activities against Class I PI3K α . MEN1611 is yellow to greenish yellow powder or powder with lumps, stable in the solid state. The MEN1611 drug product is a hard capsule for oral administration.

This study is designed as an Open-label, Multicenter, Phase Ib/II Study of MEN1611 and Cetuximab, to be conducted in approximately 29 sites in Europe and US.

Phosphatidylinositol 3-kinase, catalytic, alpha polypeptide gene (PIK3CA) mutated, N-K-RAS and BRAF wild type, metastatic colorectal cancer, in patients failing irinotecan, oxaliplatin, 5-FU and anti- epidermal growth factor receptor (EGFR) containing regimens will be enrolled.

The study is aimed to determine the RP2D of MEN1611 when administered orally in combination with cetuximab during the first step of the study, and to assess the anti-tumor activity of MEN1611 in combination with cetuximab during the second step.

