For the baseline assessment, CT scan or MRI should be performed no more than 4 weeks before the start of study treatment. Follow-up assessment will be performed every 2 cycles during study treatment starting from Day 1 Cycle 3 (within a window of 7 days before the visit date) until objective disease progression as defined by RECIST v1.1 or at the End of Study Visit. Any other site at which a new disease is suspected should be appropriately imaged. If an unscheduled assessment is performed and the disease has not progressed, subsequent assessments should be performed at their scheduled visits.

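### The SAP ties the start of Duration of Response to BOR, so on its most natural reading patients who improve from PR to CR lose their earlier time in PR

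*SAP*

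**What the plan says.** SAP 5.4.2 describes Duration of Response as "defined as time from first occurrence of a BOR of PR, CR or SD as locally assessed", running to progression. SAP 12.1 turns this into two formulas, one for progression and one for censoring. Both subtract the same start date, the "date of first occurrence of a BOR of PR, CR or SD + 1".

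SAP 12.1 derives BOR from the whole sequence of scan results and gives each patient one value. For CR the rule is "If a subject has at least one overall response of CR, then BOR is CR". For PR it is "If a subject doesn't have any overall response of CR but has at least one overall response of PR, then BOR is PR". The section uses one term for the result of a single scan (overall response) and another for the patient-level summary (BOR). The DR formulas use the second.

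Protocol 8.5.5.2 does not refer to BOR: "Duration of response defined as time from confirmation of a PR, CR or SD as locally assessed". SAP 3.1 lists departures from the protocol and says "The only exception is the PK data analysis".

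**The concern.** A duration of response should start when the response starts. Here the start depends on a summary that is known only once all scans are in. If a patient has PR and later CR, BOR is CR, so the first occurrence of the BOR is the first CR scan. The earlier time in PR then counts for nothing.

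Two patients with the same first-response date and the same progression date can therefore get different durations, with the shorter one going to the patient whose response deepened. The effect would appear in Table 3.3 and in the Kaplan-Meier curves of Figures 6.1 (local) and 6.2 (central). If local and central readers agree on first response and progression but differ on when CR began, the two DR values would differ for that reason alone.

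The wording also allows a second reading, the first scan showing any of PR, CR or SD. No sentence in the SAP chooses between them, so two programmers could produce different DR datasets from the same text.

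**Working it through.** The documents state no DR figure, so there is none to reproduce. The check applies the SAP formula to illustrative scan sequences.

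**Inputs**
- Scan schedule (SAP 5.4.2): "Follow-up assessment will be performed every 2 cycles during study treatment starting from Day 1 Cycle 3".
- Cycle length (Protocol synopsis): "Each treatment cycle will last 28 days".
- Nominal scan day for Day 1 of cycle c is 1 + 28 × (c − 1). For c = 3, 5, 7, 9, 11, 13 this gives Days 57, 113, 169, 225, 281, 337, which are 56 days apart.
- Formula (SAP 12.1): DR = PD date − start date + 1.

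**Start dates compared**
- Reading 1: first scan in the patient's BOR category.
- Reading 2: first scan showing any of PR, CR or SD.
- Reference: first scan showing CR or PR.

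**Results, PD on Day 281, best category held until then**

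| Sequence | Reading 1 | Reading 2 | Reference |
|---|---|---|---|
| PR 57, PR 113, CR 169 | 281 − 169 + 1 = 113 | 281 − 57 + 1 = 225 | 225 |
| PR 57, CR 113 | 281 − 113 + 1 = 169 | 225 | 225 |
| PR from 57 | 225 | 225 | 225 |
| SD 57, PR 113 | 169 | 225 | 281 − 113 + 1 = 169 |

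Reading 1 loses 112 days in the first row and 56 in the second. Reading 2 adds 56 days in the fourth. The third row is right on both readings.

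**Further sequences**
- SD 57, PR 113, CR 169, PD 225: Reading 1 gives 57, Reading 2 gives 169, the reference is 113. Both readings miss.
- At PD on Day 225, Reading 1 gives 57 days for PR, PR, CR but 169 for a patient with SD at all three scans. A patient with CR from the first scan also gets 169 and loses nothing.
- PR 57, CR from 113, PD 337: Reading 1 gives 225, the reference is 281. A long CR still scores long.

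**How many patients**

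The documents give no expected number of PR-to-CR patients. A rough ceiling comes from studies cited in Protocol 6.2, applied to the 40 evaluable patients in the synopsis. In the retrospective rechallenge series, 2 of 21 responders had CR. With n responders, the expected number of CRs is n × 2/21 and the chance of at least one is 1 − (19/21)^n.
- ORR 23% (prospective phase II rechallenge study): 0.23 × 40 = 9.2, so n = 9. Expected CRs 0.86; chance of at least one 0.594.
- ORR 53.8% (retrospective series): 0.538 × 40 = 21.5, so n = 22. Expected CRs 2.10; chance of at least one 0.889.

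These count any CR. Only a CR preceded by PR is affected on Reading 1, so both chances are upper bounds.

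**The case against.** The strongest case on the other side has five parts.

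- **The text has another reading.** If PR, CR and SD are simply alternatives, a PR-to-CR patient loses nothing. This stands as a limit on the claim. It does not remove the problem, because the SAP does not say which reading applies and its own BOR definition points to the first.
- **SD is in the protocol definition.** A reader might infer that the protocol starts the clock only at PR or CR. It does not; it lists SD too. Starting an SD-then-PR patient at the SD scan is therefore arguably permitted. The extra 56 days on Reading 2 are an error against first response, not clearly against the protocol. This stands.
- **An undeclared change cannot be shown.** SAP section 3 says the plan reflects protocol Version 4.0, while the protocol supplied is Version 5.0. The Version 4.0 wording for DR is not available, and the point depends on Reading 1 anyway. It carries little weight.
- **Frequency may be very low.** Another rechallenge study in Protocol 6.2 reports PR 15.6%, SD 40.6% and PD 43.8%. These sum to 100%, leaving no CR. The first-in-human study (Protocol 6.6.3) had no CR or PR. The 22-responder case borrows a response rate from a series not selected for *PIK3CA* mutation, while Protocol 6.3 and 6.5 describe such tumours as less responsive to anti-EGFR treatment. This stands.
- **A start at first CR or PR has a side effect.** It leaves SD-only patients without a start date. On the prospective study's figures, disease control 54% less ORR 23% is 31% SD, about 12 of 40 patients. The DR set would fall from about 21 (9 + 12) to 9. This stands and shapes the fix.

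**Conclusion.** The concern holds in a limited form. The DR start date is ambiguous. On the most natural reading it drops the interval from first PR to first CR: 56 days for one scan interval, 112 for two. On the other reading it starts SD-then-PR patients before they have responded, by 56 days in the example.

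A reader might infer that the deepest responders get the shortest durations. The documents do not support that as a general statement. Patients whose first response is already their best are unaffected on the first reading, and a long CR still gives a long duration. What is supported is narrower: patients whose response deepens from PR to CR lose the earlier interval, and at equal progression dates can score below patients with PR or SD only.

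The consequence is modest. DR is secondary and descriptive, its central version is exploratory, and ORR, DCR, PFS and OS do not use this start date. Few patients are expected to be affected, and no shift in the median or the curve has been calculated. With so few responders, though, one or two misdated patients could alter the DR summary.

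The day counts assume nominal visit dates. The 7-day scan window and the 5-day visit window would move them slightly. The frequency figures rest on borrowed response rates.

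**What to change.** In SAP 5.4.2 and in both DR formulas of SAP 12.1, for patients with a BOR of CR or PR, set the start to the date of the first tumour assessment with an overall response of CR or PR, whichever comes first. Apply this separately to the local and central reads.

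State explicitly what happens to patients whose BOR is SD. They have no start date under this rule, yet Protocol 8.5.5.2 includes SD. One option is a separately labelled duration of disease control. Declare the departure in SAP 3.1 and reconcile it with the protocol wording.

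No new data are needed, since response by timepoint is already planned in Listings 5.29 and 5.30. The cost is a revision of the SAP text and the derivation, a small declared departure from the protocol definition and, if SD-only patients are reported separately, a smaller DR set. It should be settled before database lock.
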